- c. **Unaccustomed Exercise Sessions (2x):** Prior to exercise training, the study will measure the response to single bouts of the training exercises before and after two weeks of nutritional supplementation. The response to exercise will be measured using both muscle and blood. The pre-exercise time points will be prior to exercise, possibly same day or a different day based on scheduling and/or the judgment of the study physician. The post-exercise time points for collection are 72 hrs for muscle and 1 hr for blood. Our studies have previously shown that 72 hrs is a better than 24 hours for measuring the immune variables of interest in muscle [52].

The 1 hr time point for blood collection is based on other studies that have determined the effects of exercise on systemic measures of immune function [11;53].

- d. **Exercise Training Sessions (36x):** The training program plans to have subjects perform supervised exercise at the NLR VA for approximately an hour optimally 3 times per week on non-consecutive days. The program consists of 36 exercise sessions that will optimally take 12-weeks though the total time will likely be longer due to rescheduling based on the needs of the subject or the study team.
- e. The exercise load will be based on how much the subject is capable of lifting one time. After strength testing, subjects will perform exercises at loads ranging from 60% to 80% (e.g. sets at 60, 70, 75, and 80% of capability) of their measured capability to the best of their ability. Strength is retested at approximately every 6th session to account for strength gain in maintaining the work load. On days of testing, the strength test replaces one of the four exercise sets. Strength is also tested twice prior to training, at the final training bout, and twice during the post-training follow-up period.
- f. Training sessions consist of three sets of 10 repetitions for each exercise and a 4th set completed at voluntary failure to complete a repetition. Subjects will rest approximately two minutes between each set and approximately 5 minutes between exercises.
- g. Exercise data will be recorded for each subject on the Exercise Data Form.

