- b. Use of Certain Medications: it is unknown how certain medications (specifically those used to control inflammation) and other age-associated medical issues will influence the variables of interest to the study. Due to this possibility, medications and medical problems will be recorded and used as potential confounding variables in the statistical or exploratory analyses.

15. Computed Tomography Scan of the Thigh

- a. **Procedure:** Muscle Cross-Sectional Area and composition will be determined by the hospital imaging service using computed tomography (CT) scan of the mid-thigh at pre-training, post-training, and at the end of the study. The service performed CT scans for our previous study which showed that size increased ($P=0.002$, $7.4 \pm 2.0\%$) in older adults after 12-weeks of

training [3]. Subjects are carefully positioned in the scanner and boney land marks are used to ensure precise mid-thigh location for each scan. Analysis of scans will be completed using a program such as Slice-O-matic (Montreal, Canada) to discern between bone, fat, and muscle.

CT scan data is transferred from the Imaging service to the study on a CD which is not encrypted per se. However, the risk of an unintended recipient accessing the data is particularly low because specialized software is required to view the data. Furthermore, the data is a cross-sectional image of the thigh which looks like a slice of ham (i.e. not sensitive). The information will be labeled with the subject study ID, not name or SSN. Transport of the disk from the LR to NLR VA will occur in a locked bag and the disks will be maintained according to CAVHS regulations.

- b. **Benefit:** The CT scan of the thigh is of no direct benefit to the subject though the measure provides important scientific knowledge of the effects of exercise training, detraining, and nutritional supplementation in older adults.
- c. **Risk:** The procedure will expose subjects to radiation. The total amount of radiation the subjects will be exposed to per scan (6 mSv) is approximately the same as the average exposure an individual has from natural sources per year. Having three scans in one year creates a very small increase (from 44.9% to 44.95%) in the risk of cancer for the average 70 year old male (www.xrayrisk.com).

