STATISTICAL PLAN: The sample size (N=50) provides greater than 80% power for Aims 1-3 to detect mean differences between groups of 0.8 to 0.85 standard deviation (SD) units at a 5% level of significance. Power calculations were based on using a one-sided t-test to compare independent groups using data from our work and others [2;23;65] though non-parametric tests or transformations will be used as necessary for data containing outliers. There is no formal plan to adjust for multiple comparisons. However, multiple correlation analysis will be used to determine the correlation between endpoints and any possible inflation in the overall Type I error rate. This analysis will allow testing of the overall hypothesis that measures of immune function (Aim 1) will be positively correlated with adaptations to exercise (Aim 2) and retention of muscle strength, mass, and function after exercise training is halted (Aim 3). The hypotheses are stated for each aim and the time points for comparison are listed in Table 6.

Aim 1 Power: Aim 1 will determine if the supplement consumption for 2-weeks improves baseline measures of immune function or the immune responses to vaccination or acute exercise. The representative measures chosen to calculate power are change in muscle macrophage content after exercise (Finding 2) and change in CRP levels post-supplementation (Pilot Study Finding 1). Przybyla et al detected a 29% increase in CD163+ macrophages in young subjects after exercise but no change in older subjects [2]. Power for this aim is calculated to detect at least a 29% greater increase in macrophages in the supplement than the placebo group. Przybyla et al used a nonparametric test to lessen the effects of outliers. To be more conservative here, the calculations here dropped the most extreme high and low data values before estimating effect sizes. With that approach, the 29% increase corresponds to an effect size of 0.8 SD units (mean/SD = 0.128/0.159). Similar results were found using CRP data from Pilot Finding 1. The effect size for change in CRP is 0.85 SD units (mean/SD = 0.665/0.780 for log-transformed data). Having at least 20 subjects per group will provide 80% or greater power to detect a mean shift of 0.8-0.85 SD units at a significance level of 5% for the following Aim 1 hypotheses:

- a. The response to vaccination will be greater in the supplement than the placebo group. The change between times K and A (Table 6) will be compared between groups.

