- b. The resting ratio of CD4+ to CD8+ t-cells will increase in the supplement but not in the placebo group. The change between times G and C will be compared between groups.
- c. The change in t-cell subsets after acute exercise will be greater in the supplement than the placebo group. The change between times I and G will be compared to the change between times E and C for both groups.
- d. Resting cytokine levels will decrease in the supplement but not in the placebo group. Change will be compared between groups for blood (times G and C) and muscle (times H and D). *Similar results are predicted for the MuRF and MAFbx atrophy-related transcripts.*
- e. The increase in cytokine levels after acute exercise will be greater in the placebo group than the supplement group. For both groups, change between times I and G will be compared to the change

Table 6. Time points are lettered for clear reference by the stated hypotheses.	
BASELINE MEASURES (WEEKS 1-5)	
A.	Blood draw at study enrollment for measuring pre-vaccination antibody titers
B.	Assessment of muscle strength, mass, and function at baseline
C.	Blood drawn prior to acute exercise at baseline
D.	Muscle biopsy prior to acute exercise at baseline
E.	Blood drawn 1 hr after acute exercise at baseline
F.	Muscle biopsy 72 hrs after acute exercise at baseline
POST-SUPPLEMENT RUN-IN MEASURES (WEEK 8)	
G.	Blood drawn prior to acute exercise after 2-weeks of supplementation
H.	Muscle biopsy prior to acute exercise after 2-weeks of supplementation
I.	Blood drawn 1 hr after acute exercise after 2-weeks of supplementation
J.	Muscle biopsy 72 hrs after acute exercise after 2-weeks of supplementation
MEASURES DURING TRAINING PERIOD (WEEKS 9-20)	
K.	Blood draws at weeks 1 and 2 post-vaccination for measuring antibody response
POST-TRAINING MEASURES (WEEK 21)	
L.	Assessment of muscle strength, mass, and function after completion of training
M.	Muscle biopsy 72 hrs after final exercise bout of training
MEASURES DURING POST-TRAINING FOLLOW-UP (WEEKS 22-4)	
N.	Assessments of strength, mass, and function after 16 and 26 weeks of detraining

between E and C for blood, and for muscle the change between times J and H will be compared to the change between times F and D.

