- f. The proliferative capacity of peripheral blood mononuclear cells will be greater in the supplement than the placebo group. The change between times G and C will be compared between groups. The change between times I and E will also be compared between groups.
- g. The resting number of muscle CD163+ macrophages will increase in the supplement but not in the placebo group. The change between times H and D will be compared between groups.
- h. The number of muscle CD163+ macrophages will increase after acute exercise in the supplement but not in the placebo group. The change between times J and H will be compared to change between times F and D for both groups.
- i. Resting NFkB activity will decrease and PI3K activity will increase in the supplement group but not in the placebo group. The change between time points H and D will be compared between groups.
- j. In response to acute exercise, NFkB activity will be lower and PI3K activity will be greater in the supplement group than in the placebo group. The change between times J and H will be compared to change between times F and D for both groups. *Responses similar to NFkB are predicted for FOXO1, and responses similar to PI3K are expected for STAT3, AKT, P38 MAPK, and ERK 1 and 2.*

Aim 2 Power: Aim 2 will determine whether supplement consumption increases muscle adaptation to 12-weeks of resistance training. The representative response measure for this objective is post-training percent increase in muscle strength. In a similar study, Trappe et al sought to improve strength gain by resistance training plus drug treatment. The drug treatment group gained significantly more strength by 25.1% than the group receiving placebo (26.4% vs. 21.1%, $P<0.05$) [23]. The previous findings presented here (Finding 4) indicate that older subjects completing a 12-week training program but not taking supplements will experience an average strength gain of $25 \pm 8\%$. If treatment with the proposed supplement improves strength similarly to the Trappe drug treatment, subjects in the supplement group will improve strength by an average of 31% (i.e., 25.1% greater than those of the placebo group). This translates to an approximate effect size of 0.8 SD units ($0.25*0.251/0.08$) if variances are pooled for the groups compared. With 20 subjects per group, there will be 80% power to detect a mean shift of 0.8 SD units using a significance level of 5% for the Aim 2 hypotheses:

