- a. The amount of strength gained from 12-weeks of training will be greater in the supplement than the placebo group. The change between times L and B will be compared between groups.
- b. The amount of muscle size gained from 12-weeks of training will be greater in the supplement than the placebo group. The change between times L and B will be compared between groups.
- c. The increase in muscle function after 12-weeks of training will be greater in the supplement than the placebo group. The change between times L and B will be compared between groups.
- d. The increase in muscle satellite cells after 12-weeks of training will be greater in the supplement than the placebo group. The change between times M and D will be compared between groups.
- e. The increase in muscle myonuclei after 12-weeks of training will be greater in the supplement than the placebo group. The change between times M and D will be compared between groups.
- f. The increase in muscle fiber size after 12-weeks of training will be greater in the supplement group than the placebo group. The change between times M and D will be compared between groups.

Aim 3 Power: Aim 3 will determine if supplement consumption increases the retention of exercise-derived benefits post-training during 26 weeks of long-term follow-up. The representative response measure for this objective is the strength gain retained during long-term follow-up after exercise training is completed. Lemmer et al observed an average gain in muscle strength of 27% ($P<0.01$) in older men after strength training which is similar the 25% gain presented here in Finding 4 [65]. However, at

31-weeks of post-training follow-up, strength had decreased to be about 9% above pre-training levels. Assuming the same level of variation among our subjects in retention of strength gain as the observed 8% SD for strength gain in Finding 4, then a 0.8 SD effect size would be about 6.4% ($0.8*0.08$), translating to our supplement group retaining strength of 12.4% above pre-training levels. With 20 subjects per group, there will be 80% power to detect a mean shift of 0.8 SD units using a significance level of 5%. If the SD for retention of strength is smaller than 8%, then we will have higher power to detect the same difference or equal power to detect smaller differences for the following Aim 3 hypotheses:

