- a. The change in strength during the detraining period will be smaller in the supplement than the placebo group. The change between times N and L will be compared between groups.
- b. The change in muscle size during the detraining period will be smaller in the supplement than the placebo group. The change between times N and L will be compared between groups.
- c. The change in muscle function will be smaller in the supplement than the placebo group. The change between times N and L will be compared between groups.

Reference List

4. Ellis A. Dietary Supplements and Aging Muscle. University of Alabama at Birmingham and the National Center for Complementary and Alternative Medicine (NCCAM) [2012 Available from: URL:<http://www.clinicaltrials.gov/ct2/results?term=NCT01057082>

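### The Aim 1-3 hypotheses compare change scores without using the outcome's own pre-product value as a covariate; this is valid, but adjusting for baselines already collected would usually be more precise at almost no cost

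*Combined protocol and SAP*

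**What the plan says.** The Aim 2 hypotheses on strength, size and function share one rule: "The change between times L and B will be compared between groups". The cellular outcomes of Aim 2 use the change from D to M. Aim 3 uses the detraining change: "The change between times N and L will be compared between groups".

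Most of Aim 1 uses a simple change from a baseline time point. Hypotheses c, e, h and j compare the acute-exercise response on product with the response before product. For T-cell subsets, for example: "The change between times I and G will be compared to the change between times E and C for both groups". Hypothesis f adds a second comparison, of post-exercise values: "The change between times I and E will also be compared between groups".

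The only test named is the one used for sample size: "Power calculations were based on using a one-sided t-test to compare independent groups". Non-parametric tests or transformations are allowed where data contain outliers.

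On covariates, section 14.b says that "medications and medical problems will be recorded and used as potential confounding variables in the statistical or exploratory analyses", and section 9.f says the change of product will be tracked to look for bias. The starting value of the outcome is not mentioned as a covariate.

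Table 6 lists time points A to F in weeks 1-5, including B, "Assessment of muscle strength, mass, and function at baseline". Section 9.c has product typically starting on the day of the second biopsy (time F). Section 10.e adds: "Strength is also tested twice prior to training, at the final training bout, and twice during the post-training follow-up period".

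**The concern.** A change score fixes the coefficient on baseline at one. If, within groups, change is still correlated with the starting value, part of its variance is predictable and is left in the error term. Noisy measurements tend to produce such a correlation, because a value that is high by chance at baseline tends to be followed by a smaller rise. Regressing the change on baseline removes that part. What is at stake is precision in a trial planned on about 20 evaluable people per group.

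Two details are also worth settling before unblinding. Strength is tested twice before training, and the plan does not say whether both tests precede the first dose. In Aim 3 the starting point L is measured on product, so an analyst who later decided to adjust for the starting value could condition on something the supplement may have changed.

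**Working it through.** **Inputs from the documents.** 20 per group, 0.8 SD of the analysed change and 5% significance (Statistical Plan, Aim 2 Power); one-sided two-sample t-test (Statistical Plan, opening paragraph).

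**Input not in the documents.** r, the within-group correlation between the analysed change and its baseline covariate. It is assumed and varied.

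**Step 1: reproduce the plan's figure.** Noncentrality = 0.8 × √(20/2) = 2.530, with 38 df. One-sided 5% power = 79.9%, matching the stated 80%.

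**Step 2: add the baseline covariate.** The variance of the group difference, relative to the change score, is (1 − r²) × (1 + 1/36). The second factor is the expected cost of estimating the slope with 40 people. The test has 37 df and noncentrality 2.530 / √[(1 − r²) × 37/36]. For example, at |r| = 0.5 the ratio is 0.75 × 1.0278 = 0.771, and the noncentrality is 2.530 / 0.878 = 2.88.

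| Assumed \|r\| | Power, adjusted | Change from 79.9% |
|---|---|---|
| 0 | 78.9% | −1.0 |
| 0.2 | 80.4% | +0.5 |
| 0.3 | 82.2% | +2.3 |
| 0.4 | 84.8% | +4.9 |
| 0.5 | 88.2% | +8.3 |
| 0.6 | 92.2% | +12.3 |

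Break-even is |r| about 0.17. Simulation of adjusted power agrees with the formula (82.2% at 0.3 and 88.1% at 0.5). In simulations with no true effect, one-sided type I error was 4.6% to 5.3% for both methods, so both are valid.

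**Step 3: what r means for a given outcome.** With equal SDs before and after, |r| = √[(1 − ρ)/2], where ρ is the baseline to follow-up correlation (also assumed). Power is then 88.2% at ρ = 0.5, 84.4% at 0.7, 80.7% at 0.9, and no better than unadjusted at about 0.95. The gain therefore belongs to measures that track poorly within a person.

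**Step 4: strength.** Take the plan's 8-point SD of gain. On the log scale, after a 25% mean gain, this is about 0.08/1.25 = 0.064. With an assumed baseline coefficient of variation of 20% or 30%, and equal log-scale SDs, ρ is 0.948 or 0.976 and |r| is √(0.052/2) = 0.16 or √(0.024/2) = 0.11. Both are below break-even. Power for the planned 6.275-point difference (0.25 × 0.251) goes from 78.6% to 78.5% or 78.0%. On the plan's own SD there is no gain for strength.

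**Step 5: outliers.** The 1-point worst case assumes roughly normal data. With heavy-tailed errors (assumed t with 3 df, 20 per group, 0.8 SD), simulated power was:

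| r | Mann-Whitney on the change | Linear ANCOVA |
|---|---|---|
| 0 | 94.6% | 83.9% |
| 0.3 | 92.1% | 85.5% |

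A rank-based ANCOVA kept about 94%. Replacing a planned non-parametric test by linear ANCOVA could thus cost about 11 points (94.6 − 83.9); a rank-based adjusted analysis does not.

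**Step 6: is B pre-product?** Table 6 puts B in weeks 1-5 and the post-supplement measures in week 8 after two weeks of product, so product starts around week 6. Figure 9 agrees: 42 product weeks ending at week 47 begin at 47 − 42 + 1 = week 6. Time B is therefore placed before product. Only the timing of the second pre-training strength test is unstated.

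**The case against.** The strongest reply is that the plan contains no error and that no gain is shown for this trial. A change from A-F already subtracts the pre-product value, every gain rests on an undocumented correlation, and for strength, the representative outcome of Aims 2 and 3, the calculation shows none. Section 14.b and the abstract's mention of multivariable testing also leave room for covariates. All of this stands, and it limits the point to an inexpensive improvement. It does not remove it: no passage names the outcome's baseline as a covariate, and the possible loss is small if the method suits the data.

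Three stronger readings are tempting, and the documents support none of them.

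- A reader might infer that the planned comparisons are biased. Under randomisation they are not.
- A reader might infer that chance baseline imbalance in a trial this small undermines the results. A change score already removes a difference in level. Imbalance matters only through the part of change that is correlated with baseline, and not at all if r = 0.
- A reader might infer that the trial has no power to spare. The 79.9% applies at exactly 20 per group and 0.8 SD. The plan says at least 20 per group and expects 40 to 50 completers; power is 87.4% at 25 per group, and 84.0% at 20 per group for the 0.85 SD effect taken from the CRP pilot data.

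**Conclusion.** The point holds as a precision improvement. The planned comparisons are valid but leave unused a covariate that is already being measured. Under the plan's own assumptions, adjustment costs 1.0 power point if r = 0 and gains 2.3 points at |r| 0.3 and 8.3 points at |r| 0.5. These figures rest on an assumed r and on roughly normal data. A gain is most plausible for the blood and biopsy measures of Aim 1 and the cellular outcomes of Aim 2. It is small or nil for strength, and for Aim 3 it may be nil, because the detraining change need not relate to the pre-product value.

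Figure 9 shows randomisation in week 1, so some baseline measures follow allocation. They are blinded and taken before product, so they remain legitimate covariates.

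**What to change.** **Aims 1 and 2.** Prespecify as the deciding analysis the between-group comparison of each stated change, adjusted for its pre-product value. Report the unadjusted comparison as supportive. Covariates:

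- Antibody titres: A.
- Strength, CT area and function: B.
- Satellite cells, myonuclei and fibre size: D.
- Resting blood or muscle measures: C or D respectively.
- Acute-exercise responses (Aim 1 c, e, h, j): the pre-product response, E−C for blood or F−D for muscle. State that biopsy F precedes the first dose.
- Second comparison in Aim 1 f: E.

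**Outliers.** Where the plan would turn to a non-parametric test, use a rank-based or robust baseline-adjusted analysis, not linear ANCOVA.

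**Strength baseline.** Name as B a strength test done before product start.

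**Aim 3.** Keep N−L as the outcome, so the question is unchanged. Adjustment is optional; if done, use B, not the on-product value L.

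**Cost.** Wording in the Statistical Plan, one degree of freedom, and about 1 power point at worst for roughly normal data. No new data, visits or participants are needed.

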- c. Supplementation will typically begin the day of the second muscle biopsy (typically Visit 5) and continue for the remainder of the participant's study involvement (optimally approximately 42 weeks). The total dosing time will likely be longer than the optimal time because scheduling of the exercise training and other appointments must be performed based on VA holidays, patient and physician availability, etc. And specific starting date or intermittent dosing lengths of time can be altered without protocol deviation in order to maintain proper spacing of the more time dependent clinical procedures, e.g. blood draw, biopsy, and vaccination.
- d. Compliance will be monitored using subject self-report and both the number of doses consumed and weight of product consumed. Each canister will contain 14 doses (7 day supply) though

this number is approximate due to the inexact measurement of one scoop. Canisters will contain 421 grams of supplement or 188 grams of placebo. Subjects will return empty containers. Containers will only be weighed if unused supplement or placebo is returned. Self-report will be based on completion and return of the dosing calendar. This information will be collected and reviewed by a study monitor, i.e. member of the study team who is not blinded. The monitor is planned to review dosing and consumption for compliance with the subject approximately every four weeks by phone or in person or more often as needed. Subject diet data will not be collected but to be involved subjects must agree to maintain their normal diet during participation.

- e. Subjects will be given a gym bag to transport their canisters of supplement/placebo and consumption calendar between home and study visits. They will also be given two drink mixer bottles of the type commonly used to mix powder shakes. These products contain the GRECC name and phone number of the study coordinator. Subjects will be allowed to keep the bag and bottles upon completion of the study. The approximate value of the products per subject is ~\$28. These gifts are justified due to making it easier for the subject to transport materials to and from study visits which should increase subject compliance with dosing and monitoring requirements.

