- h. Exceptions to the plan for each subject to complete 36 exercise training sessions may be necessary on a case-by-case basis at the discretion of the PI in order to ensure that the final muscle biopsy of the protocol occurs 72 hours (3 days) after the final exercise training session. Addition or subtraction of a limited number (optimally 1-2) of exercise sessions may be necessary to meet this time frame due to scheduling difficulties for the biopsy. Scheduling obstacles include physician or subject availability or more commonly the fact that the final exercise session cannot fall on a Wednesday or Thursday unless plans are made to perform the biopsy on Saturday or Sunday which is not preferable. Maintaining this time frame for biopsy is the priority as it has a greater chance of influencing the cellular measurements to be made using the biopsy than would a small difference in the total number of exercise sessions for influencing strength gain over the long training period.
- i. **Benefit:** Regular resistance exercise is an effective method for improving many aspects of health and well-being (13). Subjects will likely improve the size (CT scan), strength (strength testing), and function (see below) for their thigh muscles. The assessments of muscle function include:
 - (1) Berg Balance Scale (BBS): BBS is used to detect balance impairments in older adults while the individual is static or performing various movements [53]. The test consists of 14 tasks performed in standardized order and the results have been shown to have good inter-rater reliability of 0.98.
 - (2) Six Minute Walk Test (6MWT): The test is used to measure mobility performance in older adults and individuals with limitations [54]. The subjects will perform a supervised timed walk on a 200 foot track at a pace without encouragement and which allows speech without shortness of breath.
 - (3) Gait Speed: The test measures habitual walking speed [55]. The subjects will walk at their normal preferred pace for 14 meters though only the middle 10 meters are timed. The result is an average of three replicates.

- (4) Timed Up and Go: The test is indicative of balance and mobility by a measuring the time required for the subject to rise from a chair, walk three meters, turn around, walk back to the chair, and sit down [55].
- (5) Functional assessment data will be collected at four times during the protocol: pre-training, post-training, during post-training follow-up, and at end of study.

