- a. The study did consider the ethical issue of disallowing resistance training of the thighs during the post-training period since the benefits of the exercise training will be partially lost without it. We concluded that this criterion was acceptable because it eliminates a strong confounder (i.e. strength training) for Aim 3 (Does the supplement promote retention of the benefits of exercise?) of the study; older adults are unlikely to participate in high-intensity training of the thighs anyway; and other options in exercise more commonly practiced by older adults are acceptable as an alternative.

12. Muscle Biopsy: Muscle biopsy is a procedure commonly performed in physiology studies. The studies involving this PI have collected several hundred biopsies from the thigh. Only three problems have occurred which involved resumption of bleeding that required a pressure bandage, a mild reaction to the lidocaine injection which resulted in halting of the procedure, and fainting which led to withdrawal of the subject from the study.

- a. **Procedure:** Muscle tissue will be obtained from each subject by needle biopsy of the vastus lateralis (outer thigh) by a study physician. Each subject will undergo the procedure five times. The first four will occur before and 72 hrs after a single bout of exercise completed before and after approximately 2-weeks of consuming the supplement or placebo. The final biopsy will occur 72 hrs after completion of the exercise training program. The procedure is performed after local anesthetic (lidocaine) is used to numb the site. A small incision will be made in the skin and a Bergstrom needle will be inserted briefly into the muscle to remove several pea-sized pieces of muscle (7). Direct pressure will be applied to stop the bleeding. The wound is closed with a band-aid type bandage and covered with a pressure bandage. The procedure will be performed according to an approved Muscle Biopsy SOP. The procedure details and outcomes will be documented using the Subject Procedure Note. Pre-exercise biopsies will be taken from the dominant leg while post-exercise biopsies will be taken from the non-dominant leg.

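### Aim 2 cellular endpoints: the raw change from biopsy D to biopsy M is noisier than it needs to be and mixes training with leg and acute-exercise effects; adjust for D by ANCOVA and use biopsy F in support

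*Combined protocol and SAP*

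**What the plan says.** In the Statistical Plan, hypotheses d, e and f of Aim 2 each end with the same sentence: "The change between times M and D will be compared between groups". No other baseline biopsy is named for these three endpoints.

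Table 6 defines the biopsies that matter here:

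- D: "Muscle biopsy prior to acute exercise at baseline".
- F: "Muscle biopsy 72 hrs after acute exercise at baseline".
- M: "Muscle biopsy 72 hrs after final exercise bout of training".

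Section 12 (Muscle Biopsy), item a, repeats the timing of the last one, "The final biopsy will occur 72 hrs after completion of the exercise training program", and gives the leg rule: "Pre-exercise biopsies will be taken from the dominant leg while post-exercise biopsies will be taken from the non-dominant leg".

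Section 10, item h, lets the number of training sessions vary so that the last biopsy keeps its 72-hour interval. The reason given for that timing is that "it has a greater chance of influencing the cellular measurements to be made using the biopsy" than a small difference in session count has of influencing strength gain.

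Under Supplementation, item c, dosing typically starts on the day of the second biopsy, which is F, but the start date may be moved without a protocol deviation. The plan uses F only in the Aim 1 acute-exercise contrasts.

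**The concern.** Going from D to M, three things change: training status, time since exercise (rested against 72 hours after a bout) and, on the natural reading of the leg rule, the leg. Only the first is what hypotheses d to f are about. The protocol itself treats time since exercise as able to move cellular measurements, yet it neither explains the choice of a rested sample as sole reference nor plans any analysis that accounts for the difference.

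Two things are at stake. One is precision: an unadjusted change score carries the full noise of the baseline sample, including leg and acute-response variation between subjects. The other is interpretation. The size of the increase reported within each arm is not purely a training effect. The plan also correlates Aim 1 immune measures with Aim 2 adaptations subject by subject, and randomization does not remove a leg or acute-exercise component from those correlations.

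**Working it through.** **Biopsy map** (Table 6, section 12.a, Supplementation item c)

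| Biopsy | Leg | Time since exercise | Product |
|---|---|---|---|
| D | dominant | rested | before |
| F | non-dominant | 72 h after one unaccustomed bout | typically before |
| M | non-dominant (inferred) | 72 h after last training bout | on product |

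M minus D differs in leg and time since exercise as well as training. M minus F matches on both, but the bout before F is a first bout in untrained muscle.

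**The plan's own figure.** Inputs from the Statistical Plan: 20 per group, 0.8 SD, 5%, one-sided t-test, stated power 80%. The noncentral t with 38 df gives 0.799 and the normal approximation 0.812, so the figure reproduces. It does not depend on which biopsy is the baseline, because the effect is expressed in SD units.

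**What cancels.** Let a leg or acute offset o be the same in both arms. The between-arm difference in M minus D is (effect in supplement arm + o) − (effect in placebo arm + o), and o drops out. On a percent scale, which the Fiber Size paragraph uses, a common proportional offset rescales the difference without creating one. With an assumed 10% offset, true gains of 15% and 10% become 1.10 × 1.15 − 1 = 26.5% and 1.10 × 1.10 − 1 = 21.0%, a difference of 5.5 points rather than 5.

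**Precision.** The documents give no between-biopsy correlations, so the values here are assumptions: unit variance at each biopsy, r(M,D) = 0.4, r(D,F) = 0.5.

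- Change score: Var(M − D) = 2(1 − 0.4) = 1.20.
- ANCOVA on D: 1 − 0.4² = 0.84.
- ANCOVA on D and F, with r = r(M,F): R² = (0.4² + r² − 2 × 0.4 × r × 0.5) / (1 − 0.5²) = (0.16 + r² − 0.4r) / 0.75, and residual variance is 1 − R².

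| r(M,F) | R² | Residual variance, D and F | Var(M − F) = 2(1 − r) |
|---|---|---|---|
| 0.6 | 0.28/0.75 = 0.373 | 0.63 | 0.80 |
| 0.5 | 0.21/0.75 = 0.280 | 0.72 | 1.00 |
| 0.4 | 0.16/0.75 = 0.213 | 0.79 | 1.20 |
| 0.3 | 0.13/0.75 = 0.173 | 0.83 | 1.40 |
| 0.2 | 0.12/0.75 = 0.160 | 0.84 | 1.60 |

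In the most favourable row the total fall is 1.20 − 0.63 = 0.57. Of that, 1.20 − 0.84 = 0.36, or 63%, comes from replacing the change score by ANCOVA on D and owes nothing to F.

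**In power terms.** Suppose M minus D has an effect of 0.8 SD and power 0.80. The same absolute difference under ANCOVA on D is 0.8 × √(1.20/0.84) = 0.96 SD, with power 0.91 (37 df). Adding F gives 0.96, 0.94, 0.92 or 0.91 for r(M,F) = 0.6, 0.5, 0.4 or 0.2 (36 df).

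**The case against.** The strongest case for the plan is that hypotheses d to f compare randomized arms. The exercises are bilateral (section 10.a), so the leg difference is one of dominance, not trained against untrained. D is also the one biopsy taken before both any study bout and any product, which makes it a defensible reference for an increase after training. All of this stands.

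A reader might go further and infer that M minus D gives a biased treatment comparison and that F is the correct baseline. The documents do not support that, for five reasons:

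- Offsets common to both arms cancel, as shown above.
- M's leg is inferred. Section 12.a describes the first four biopsies as pairs around a single bout and mentions the last one separately.
- F matches M on hours since exercise but not on stimulus, since it follows an unaccustomed bout. If that first bout raises a marker more than an accustomed one does, M minus F understates the training change.
- F is only typically taken before product. Where dosing came first, adjusting for F could remove part of the supplement effect.
- A between-arm bias would need the supplement to alter the acute response at M. If that response differed by 0.2 SD of change with no true training effect, the one-sided rejection rate would be 15% instead of 5%. A pre-supplement F cannot remove this, so M minus F would carry it too.

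Nor is it documented that F predicts M better than D does. If r(M,F) is below 0.4 under these assumptions, M minus F is noisier than M minus D.

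**Conclusion.** The concern holds as a matter of precision and interpretation, not validity. The between-arm test of M minus D is sound on the absolute scale. It is less precise than a baseline-adjusted analysis of the same data: residual variance 1.20 against 0.84 at an assumed M-D correlation of 0.4. Adding F lowers 0.84 further to 0.63 at r(M,F) = 0.6 and not at all at 0.2. These sizes rest on assumed correlations and equal variances.

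The within-arm increase after training, and its correlation with immune measures, should not be read as a pure training effect. The point touches only the three cellular endpoints of Aim 2. Strength, CT muscle size, function and the sample size are unaffected. It is an inexpensive improvement rather than a necessary correction.

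**What to change.** 1. Make the main analysis of hypotheses d to f an ANCOVA of the M value on arm with D as baseline covariate, in place of the raw change. This costs one degree of freedom and no laboratory work.
2. State which leg biopsy M comes from.
3. Where tissue allows, count satellite cells, myonuclei and fibre size on biopsy F as well. Prespecify a supportive analysis that adds F as a second covariate and reports M minus F beside M minus D, restricted to subjects whose F preceded the first dose.
4. State in the plan that F follows an unaccustomed bout, so M minus F is not a pure training effect, and that it does not remove any supplement effect on the acute response. Attach a matching caution to the within-arm M minus D changes and to the correlations with immune measures.

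No new biopsy, visit or change in sample size is needed, and F is already to be sectioned for the Aim 1 macrophage counts. The cost of step 3 is microscopy on three biopsies per subject instead of two for these markers, plus one further degree of freedom. Tissue sufficiency is not documented, since the same biopsies also supply the RNA and signalling assays. That is why step 3 is supportive and conditional on tissue.
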